9.4.3 Formulation and Stability

Fludarabine phosphate injection is available as sterile lyophilized powder and in solution. Each single-dose vial of powder contains 50 mg of the active ingredient fludarabine phosphate, 50 mg of mannitol, and sodium hydroxide to adjust the pH to 7.7. After reconstitution, the pH range for the final product is 7.2-8.2. The single-dose solution vial contains 25 mg/mL, 2 mL of fludarabine phosphate. It may contain mannitol and is preservative-free.

Fludarabine phosphate vials should be stored refrigerated at 2-8°C (36-46°F).

9.4.4 Guidelines for Administration

See Treatment and Dose Modification sections of the protocol.

Fludarabine phosphate powder should be reconstituted with 2 mL of Sterile Water for Injection. The solid cake should fully dissolve in 15 seconds or less. The resulting concentration is 25 mg/mL. When reconstituted to a final concentration of 25 mg/mL, the drug is stable for at least 16 days at room temperature and normal light conditions. The manufacturer recommends that the solution be used within 8 hours after reconstitution.

Prior to administration, fludarabine 25 mg/mL solution or the reconstituted 25 mg/mL solution should be further diluted in 100 mL or 125 mL of D5W or NS. Concentrations of 0.25 to 1 mg/mL have been used in clinical trials. When diluted to a final concentration of 1 mg/mL, fludarabine is stable for at least 16 days at room temperature and normal light conditions. The manufacturer recommends that the diluted solution be used within 8 hours after preparation. Parenteral drug products should be inspected visually for particulate matter and discoloration prior to administration.

9.4.5 Supplier:

Commercially available from various manufacturers. See package insert for further information.

9.5 **Intrathecal Triples (Methotrexate/Hydrocortisone/Cytarabine, IT-3) (05/08/12)**

9.5.1 Source and Pharmacology

The intrathecal route of administration of a drug produces more consistent CSF drug concentrations at relatively smaller doses because of the volume difference between the CSF and blood compartments (140 mL vs. 3500 mL in an adult). (The CSF volume of children after the first 3 years is equivalent to that of an adult). Drug half-lives are longer as well because clearance is related to flow rather than metabolism or protein binding. Intrathecal methotrexate has a biphasic elimination curve from the CSF with a $t_{1/2}$ of 4.5 and 14 hours respectively. Following IT injection of cytarabine the elimination of the drug from the CSF is biphasic with a $t_{1/2}$ of 1 and 3.4 hours respectively which is 8-fold longer than the clearance from plasma. The elimination of hydrocortisone is similarly prolonged.

9.5.2 Toxicity

Intrathecal Triple Therapy (Methotrexate/Hydrocortisone/Cytarabine) Toxicity:

	Common Happens to 21-100 children out of every 100	Occasional Happens to 5-20 children out of every 100	Rare Happens to < 5 children out of every 100
Immediate: Within 1-2 days of receiving drug	Nausea, vomiting, fever, headache	Arachnoiditis: (headache, fever, vomiting, meningismus and pleocytosis)	Rash, anaphylaxis (L), paresis, bleeding into subarachnoid or subdural space (risk > with platelet counts <20,000), confusion, fatigue, disorientation, seizures
Prompt: Within 2-3 weeks, prior to the next course			Myelosuppression, somnolence, ataxia, cranial nerve palsy, transient and rarely permanent paraplegia (L), speech disorders
Delayed: Any time later during therapy, excluding the above condition		Cognitive disturbances (L), learning disabilities (L)	Demyelinating leukoencephalopathy ¹ (L), blindness ¹
Late: Any time after the completion of treatment			Progressive CNS deterioration ¹

¹ May be enhanced by systemic therapy such as high dose methotrexate or cytarabine and/or cranial irradiation.

(L) Toxicity may also occur later.

9.5.3 Formulation and Stability

Methotrexate 25 mg/mL preservative free 2 mL vial or methotrexate 20 mg preservative free sterile powder for injection vial. Cytarabine 100 mg preservative free sterile powder for injection. Hydrocortisone sodium succinate 100 mg vial sterile powder for injection.

9.5.4 Guidelines for Administration

See Treatment and Dose Modification sections of the protocol.

For intrathecal administration, dilute each agent with 5-10 mL preservative free NS, lactated ringers or Elliot's B solution or as per institutional standard of

practice. The volume of CSF removed should be equal to at least half the volume delivered.

Patient Age (years)	Doses (MTX/Hydrocortisone/Ara-C)	Recommended volume	10% CSF volume	CSF Volume *
0 – 0.99	7.5 mg / 7.5 mg / 15 mg	5-10 mL	5 mL	50 \pm 10 mL (babies)
1 – 1.99	8 mg / 8 mg / 16 mg	5-10 mL	5 mL	50 \pm 10 mL (babies)
2 – 2.99	10 mg / 10 mg / 20 mg	5-10 mL	8 mL	80 \pm 20 mL (younger children)
3 – 8.99	12 mg / 12 mg / 24 mg	5-10 mL	10 mL	100 \pm 20 mL (older children)
9 or greater	15 mg / 15 mg / 30 mg	5-10 mL	13 mL	130 \pm 30 mL (adults)

*Rieselbach, R.E. et.al. Subarachnoid distribution of drugs after lumbar injection. *N Engl J Med* 1962 Dec 20; 267:1273-8

Of note: Larger volumes approximating at least 10% of the CSF volume, isovolumetric delivery, with the patient remaining prone after the procedure may facilitate drug distribution. These procedures have not been validated in clinical trials. They are allowed but not mandated for patients on COG studies.

Intrathecal triples are stable in NS for 24 hours at 25°C but contain no preservative and should be administered as soon as possible after preparation.

9.5.5 Supplier

Commercially available from various manufacturers. See package insert for further information.

10.0 CRITERIA FOR REMOVAL FROM PROTOCOL THERAPY AND OFF STUDY CRITERIA

10.1 Criteria for Removal from Protocol Therapy

- a) Evidence of treatment failure (See [Section 12.2.5](#)).
- b) Adverse Events requiring removal from protocol therapy (See [Section 6](#)).
- c) Refusal of protocol therapy by patient/parent/guardian
- d) Non-compliance that in the opinion of the investigator does not allow for ongoing participation.
- e) Completion of 2 cycles of therapy.
- f) Physician determines it is not in the patient's best interest.
- g) Repeated eligibility laboratory studies (CBC with differential, bilirubin, ALT (SGPT) or serum creatinine) are outside the parameters required for eligibility prior to the start of MLN4924 (pevonodistat) (See [Section 8.1](#)).
- h) Study is terminated by Sponsor.
- i) Pregnancy

Patients who are removed from protocol therapy during Cycle 1 should continue to have the required observations in [Section 8.1](#) until the originally planned end of the cycle or until all adverse events have resolved per [Section 13.4.4](#), whichever happens LATER. The only exception is with documentation of the patient's withdrawal of consent. Patients who are removed from protocol therapy in subsequent cycles should have the necessary observations to ensure adequate clinical care.

Patients who are off protocol therapy are to be followed until they meet the criteria for Off Study (see below). Ongoing adverse events, or adverse events that emerge after the patient is removed from protocol therapy, but within 30 days of the last dose of investigational agent, must be followed and reported via RAVE and CTEP-AERS (if applicable). Follow-up data will be required unless consent is withdrawn.

10.2 Off Study Criteria

- a) Thirty days after the last dose of the investigational agent.
- b) The patient does not receive protocol treatment after study enrollment.
- c) Death
- d) Lost to follow-up
- e) Withdrawal of consent for any required observations or data submission.
- f) Enrollment onto another COG therapeutic (anti-cancer) study

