NOTE: Central venous access in the form of a double lumen Broviac or Hickman is highly recommended.

	Day 0	1	2	3	4	5	6	7	8	9	10	11-34	35
IT Cytarabine (all patients)	X												
Azacitidine		X	X	X	X	X							
MLN4924 (Pevonedistat)		X		X		X							
Fludarabine							X	X	X	X	X		
Cytarabine							X	X	X	X	X		
IT Cytarabine OR ITT* (CNS2/3)									X*			X*	

*For patients with CNS 2/3 status, IT cytarabine or ITT should be administered 2x/weekly until the CNS is clear of blasts on 2 consecutive LPs, with a minimum of 4 IT cytarabine/IT triple doses administered. This should begin on Day 8 and should be repeated 2x/weekly with not less than 3 days between doses, thus any necessary subsequent doses should be given starting on Day 11. Days of therapy may vary depending on scheduling.

A cycle of therapy is considered to be 35 days. A cycle may be repeated for a total of 2 cycles, up to a total duration of therapy of approximately 4 months.

Drug doses of MLN4924 (pevonedistat), azacitidine, fludarabine, and cytarabine should be adjusted based on the BSA calculated from height and weight measured within 7 days prior to the beginning of each cycle. Drug doses of intrathecal cytarabine and intrathecal triples should be based on the age at the time of administration.

See [Appendix VIII](#) for Therapy Delivery Maps for each cycle.

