Starting dose: 20 mg/m² for patients ≥ 1 year of age; 15 mg/m² for patients < 1 year of age (Dose Level 1). See Dosing Schema in [Section 5.4](#).***NOTE:** Give MLN4924 (pevoneditat) 30 – 60 minutes after the completion of the azacitidine infusion. If MLN4924 (pevoneditat) dosing is delayed, a minimum of 1 full calendar day between any 2 doses should be maintained.**Fludarabine: IV over 30 minutes once daily**

Days: 6-10

Dose: Age based dosing

Age	Dose
< 1 year	1 mg/kg/dose
≥ 1 year	30 mg/m ² /dose

High Dose Cytarabine: IV infusion over 1-3 hours once daily

Days: 6-10

Dose: Age based dosing (begin 4 hours after start of fludarabine)

Age	Dose
< 1 year	67 mg/kg/dose
≥ 1 year	2000 mg/m ² /dose

Please note: Following/during high-dose cytarabine, chemical conjunctivitis may occur. Administer steroid eye drops (0.1% dexamethasone or 1% prednisolone ophthalmic solution), 2 drops to each eye every 6 hours, beginning immediately before the first dose and continuing for 24 hours after the last dose. If patient does not tolerate steroid eye drops, artificial tears may be administered on an every 2-4 hour schedule.

See the Chemotherapy Administration Guidelines (CAG) on the COG website at: https://cogmembers.org/_files/disc/Pharmacy/ChemoAdminGuidelines.pdf for special precautions and suggestions for patient monitoring during the infusion. As applicable, also see the CAG for suggestions on hydration, or hydrate according to institutional guidelines.

5.3**Criteria for Starting Cycle 2**

Patients may proceed to cycle 2 following completion of cycle 1 disease assessment if stable or greater response and if non-hematologic toxicities probably or definitely related to MLN4924 (pevoneditstat) recover to \leq grade 2. Bilirubin, ALT, and AST must be \leq Grade 1 or at the patient's baseline values prior to starting Cycle 2.

NOTE: See [Appendix III](#) for Toxicity Specific Grading.

- Patients will have disease assessment on Day 36-39 of Cycle 1. If a bone marrow aspirate cannot be evaluated (dry tap, no spicules), a follow-up bone marrow aspirate and biopsy must be performed within 2 weeks to assess cellularity and response.
- If aspirate and/or biopsy results indicate hypocellular marrow (<10% cellularity on biopsy), then continue to repeat bone marrow aspirate and/or biopsy not less than once every 14 days until response can be assessed.

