12.2 Response Criteria for Patients with Leukemia

12.2.1 Complete Remission (CR)

Attainment of an M1 bone marrow (< 5% blasts and adequate marrow cellularity) with no evidence of circulating blasts or extramedullary disease and with recovery of peripheral blood counts (ANC \geq 1000/uL and platelet count \geq 100,000/uL). Flow cytometry may be useful to distinguish between leukemia and a regenerating bone marrow. There is no requirement for bone marrow cellularity.

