12.2.6 Relapse

Morphologic relapse after CR/CRp/CRi is defined as a reappearance of leukemic blasts in the peripheral blood or $\geq 5\%$ blasts in the bone marrow not attributable to any other cause (e.g. bone marrow regeneration after therapy). In the setting of recent treatment, if there are no circulating blasts and the bone marrow contains 5-20% blasts, a repeat bone marrow performed at least a week later is necessary to distinguish relapse from bone marrow regeneration. Should flow cytometric or molecular analyses suggest relapse (by reappearance of similar immunophenotype or mutation to the original leukemia) in the presence of $< 5\%$ blasts or $\geq 5\%$ blasts in a regenerating marrow, a repeat bone marrow performed at least a week later is necessary to confirm relapse by morphologic methods. In such instances, the date of recurrence is defined as the first date that more than 5% blasts were observed in the bone marrow. The reappearance or development of cytogenetically proven extramedullary disease also indicates relapse. Molecular and/or genetic relapse is characterized by reappearance of a cytogenetic or molecular abnormality.

12.2.7 Unevaluable:

Aplastic or severely hypocellular marrow. In this instance, marrow evaluation should be repeated weekly until response determination can be made through at least Day 60.

12.2.8 Bone Marrow Classification:

- M1 is $< 5\%$ blasts
- M2 is 5-25% blasts
- M3 is $> 25\%$ blasts

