Cytarabine	IV over 1-3	Age-based dosing:	6-10	Use eye drops as described in Section 5.2 .

ADVL1712

THIS PROTOCOL IS FOR RESEARCH PURPOSES ONLY, SEE PAGE 1 FOR USAGE POLICY

(ARAC)	hours	Age (yrs)	Dose			To begin 4 hours after the start of the fludarabine infusion.
		< 1	67 mg/kg/dose			

Ht _____ cm Wt _____ kg BSA _____ m² Dose Level _____ mg/m²

Date Due	Date Given	Day	IT ARAC _____ mg	AZA _____ mg	MLN4924 (Pevonedistat) _____ mg	FLU _____ mg	ARAC _____ mg	Studies
Enter calculated dose above and actual dose administered below								
		Pre-	_____ mg					a - f, h, i, k
		1		_____ mg	_____ mg			g, l
		2		_____ mg				
		3		_____ mg	_____ mg			g, l
		4		_____ mg				
		5		_____ mg	_____ mg			g, l
		6				_____ mg	_____ mg	
		7				_____ mg	_____ mg	
		8				_____ mg	_____ mg	
		9				_____ mg	_____ mg	
		10				_____ mg	_____ mg	
		11						
		12						
		13						
		14						
		15						
		16						
		17						
		18						
		19						
		20						
		21						
		22						g

THIS PROTOCOL IS FOR RESEARCH PURPOSES ONLY, SEE PAGE 1 FOR USAGE POLICY

		23									
		24									
		25									
		26									
		27									
		28									
		29									
		30									
		31									
		32									
		33									
		34									
		35									h – k

Required Observations in Cycle 2

- a. Hx/Wt /Ht/BSA. Prior to Cycle 2.
- b. Physical exam (including VS). Prior to Cycle 2.
- c. CBC/diff/platelets. Prior to Cycle 2.
- d. Electrolytes including Ca⁺⁺, Mg⁺⁺, PO₄. Prior to Cycle 2.
- e. Creatinine. Prior to Cycle 2.
- f. Albumin. Prior to Cycle 2.
- g. ALT, AST, Bilirubin. Prior to each dose of MLN4924 (pevonedistat), then weekly.
- h. ECHO or gated radionuclide study. Prior to Cycle 2 and at the end of Cycle 2.
- i. EKG. Prior to Cycle 2 and at the end of Cycle 2.
- j. Bone marrow aspirate and/or biopsy. At the end of Cycle 2.
- k. CSF for cell count, cytopspin. With day 0 IT and at the end of Cycle 2.
- l. Vital signs. Prior to each dose of MLN4924 (pevonedistat).

This listing only includes evaluations necessary to answer the primary and secondary aims. OBTAIN OTHER STUDIES AS REQUIRED FOR GOOD CLINICAL CARE.

ADVL1712

THIS PROTOCOL IS FOR RESEARCH PURPOSES ONLY, SEE PAGE 1 FOR USAGE POLICY

Comments

(Include any held doses, or dose modifications)

Cycle 2

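### After Cycle 2, the off-study rule ends follow-up on Day 35, 25 days short of the Day 60 through which the plan repeats an unevaluable marrow

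*Combined protocol and SAP*

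**What the plan says.** - **Off study.** Section 10.2(a) sets the limit at "Thirty days after the last dose of the investigational agent". Section 10.1 applies the off-study criteria to patients who have already left protocol therapy, and item (e) counts completing two cycles as leaving it.
- **Dosing and cycle length.** Section 5.2 gives pevonedistat on Days 1, 3 and 5. Section 5.1 says "A cycle of therapy is considered to be 35 days".
- **Response marrow.** For Cycle 1, Section 5.3 says "Patients will have disease assessment on Day 36-39 of Cycle 1". For Cycle 2, the delivery map in Appendix VIII-B says "Bone marrow aspirate and/or biopsy. At the end of Cycle 2" and charts it on the Day 35 row.
- **Repeat marrows.** Section 12.2.7 says that, when the marrow is aplastic or severely hypocellular, "marrow evaluation should be repeated weekly until response determination can be made through at least Day 60". It is not limited to one cycle. Section 5.3, which deals with entry to Cycle 2, says of a hypocellular marrow to "continue to repeat bone marrow aspirate and/or biopsy not less than once every 14 days until response can be assessed".
- **Counts.** Section 12.2.1 defines CR as an M1 marrow "with recovery of peripheral blood counts" (ANC at least 1000/µL, platelets at least 100,000/µL). CRp (12.2.2) needs the same ANC and a week free of platelet transfusion. CRi (12.2.3) is the category for an M1 marrow with incomplete counts.
- **Observation after removal.** Under Section 10.1, a patient removed during Cycle 1 keeps the Section 8.1 observations to the cycle's scheduled end or to adverse-event resolution, whichever is later. For removal in a later cycle it asks only for what clinical care needs.

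**The concern.** The off-study rule is tied to the last pevonedistat dose, which falls early in the cycle. The response rules are tied to marrow and count recovery, which come late. After the final cycle, two sections therefore set different end dates for the same endpoint, and nothing says which prevails.

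Antitumor activity is the only secondary aim (Section 1.2), and Section 2.5 looks ahead to a phase 2 efficacy trial based on this study's results. If a site closes follow-up under 10.2(a), a patient whose marrow is hypocellular at the end of Cycle 2 has no route to a response category. A patient with an M1 marrow and slow counts keeps whatever category the counts gave on Day 35.

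**Working it through.** The plan states no off-study day, so there is no figure to reproduce. The check is calendar arithmetic. I assume that Day 60 in 12.2.7 counts from Day 1 of the cycle being assessed, which the section does not say.

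Off-study day = day of last pevonedistat dose + 30.

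| Last pevonedistat dose | 30 days end | Against charted Cycle 2 marrow (Day 35) | Against Day 60 |
|---|---|---|---|
| Day 5 (as planned) | 5 + 30 = Day 35 | same day | 60 − 35 = 25 days short |
| Day 3 (Day 5 held) | 3 + 30 = Day 33 | 2 days before | 27 days short |
| Day 1 (Days 3 and 5 held) | 1 + 30 = Day 31 | 4 days before | 29 days short |

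**Can a delayed dose close the gap?** Reaching Day 60 would need a last dose on Day 60 − 30 = Day 30. No plausible delay of a Day 5 dose does that.

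**What falls in the gap?** Weekly repeats after an unevaluable Day 35 marrow would fall on Days 42, 49 and 56. All three come after the off-study day.

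**Does another clause cover it?**
- After Cycle 2, 10.1(e) has already put the patient off protocol therapy, so 10.2(a) governs.
- The 10.1 extension is confined to removal during Cycle 1. Its scheduled-end limb stops at Day 35, which is 1 to 4 days before a Day 36-39 marrow. Only an unresolved adverse event carries it further.
- Section 10.1 also says follow-up data are required unless consent is withdrawn. That sentence gives no duration and follows the one that ends follow-up at the off-study criteria.

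**Are the counts collected?** The Cycle 2 delivery map lists the CBC only before Cycle 2. Transfusion status, which CRp depends on, is not among its required observations. So even the Day 35 marrow has no scheduled counts with which to assign CR, CRp or CRi.

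**What does one lost patient do?** The plan does not say how unevaluable patients enter a response rate. If they count as non-responders among the 23 patients anticipated in Section 11.1, each one moves the rate by 1/23 = 4.3 percentage points. Among the absolute maximum of 38 it is 1/38 = 2.6 points. These are per-patient effects, not an estimate of how many patients are affected.

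**The case against.** The strongest reply is that the primary response marrow is usually safe, and that stands.

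- A reader might infer that 10.2(a) removes every patient before the Day 36-39 marrow. The documents do not support that. The window is stated for Cycle 1 only, and a patient awaiting that marrow has normally met no removal criterion in 10.1, so the off-study criteria do not yet apply. Otherwise every patient would leave the study before the marrow that decides entry to Cycle 2. The exposed Cycle 1 patients are those removed before that marrow.
- For those patients the 10.1 extension can do real work. Unresolved cytopenia recorded as an adverse event would prolong observation, so it is not shown that the loss in this group falls mainly on the most myelosuppressed.
- A held pevonedistat dose does not by itself end protocol therapy, because Section 6.3.5 continues azacitidine and can allow the later drugs. This stands too, but it offers little protection. The 30 days have then already expired when Cycle 2 ends, which leaves no off-therapy follow-up at all.
- An M1 marrow with incomplete counts is not unscorable, because CRi exists for it. Moving a patient between CR and CRi leaves a pooled CR/CRp/CRi count unchanged.
- Response is a secondary aim, reported descriptively (Section 11.5). No sample size, dose decision or error rate depends on it.

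None of this answers the conflict with 12.2.7 after Cycle 2.

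**Conclusion.** The conflict is real but limited. For a patient who completes Cycle 2 with the planned Day 5 dose, follow-up ends on the day the marrow is charted and 25 days before the repeat-marrow period in 12.2.7 may end. With held doses the 30 days end 2 or 4 days before the charted marrow. Patients removed during Cycle 1 before their marrow are covered only to Day 35 or adverse-event resolution. What can be lost is a late response after an unevaluable marrow, and the later counts that would separate CR or CRp from CRi.

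The size of the loss cannot be estimated reliably. A reader might take the medians of 38 and 37 days in Section 2.1, read the 50-day figure as two standard deviations (SD 6 or 6.5), assume normality, and obtain 31% to 38% recovered by Day 35, or 9% to 14% if recovery is timed from Day 6. It would then be tempting to call most final-cycle M1 marrows unclassifiable. That does not follow. The figures rest on one approximate sentence about another trial and use thresholds below those for CR, and slow counts give CRi, not a missing category. They show only that recovery after Day 35 is to be expected.

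**What to change.** **Section 10.2(a).** State that the patient goes off study at the later of:

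(i) 30 days after the final pevonedistat dose; and
(ii) the earliest of response determination for the last cycle, Day 60 of that cycle, or start of other anti-leukemic therapy.

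Placing new therapy inside (ii) means that it ends only the response follow-up and never shortens the 30-day safety follow-up. The other off-study criteria stay as they are.

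**Section 10.1.** Amend the sentence on removal in subsequent cycles, which now asks only for observations needed for care, so that it agrees with the new 10.2(a). Say also that the Cycle 1 extension runs to the same response stop.

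**Section 8.1 and Appendix VIII-B.** Add end-of-Cycle-2 counts and platelet-transfusion status to the recorded data, continuing to the stop in (ii), so that CR, CRp and CRi can be assigned.

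**Cost.** An amendment to three places, and up to about 25 more days of data submission for some patients (27 or 29 where doses were held). The repeat marrows are already required by 12.2.7. The added data are the Cycle 2 counts and transfusion status. No dose or treatment rule changes.
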